6 TREATMENT PLAN

6.1 Dosing and Administration

The treatment regimen to be used in this trial is outlined below:

Cetuximab 400 mg/m² loading dose on day 1 cycle 1, followed by 250 mg/m² intravenously weekly. Pembrolizumab 200 mg fixed dose intravenously every 3 weeks.

Reported adverse events (AEs) and potential risks are described in **Section 1.5**. Appropriate dose modifications are described in **Section 6.1**

A cycle is defined as 3 weeks of treatment, with cetuximab administered weekly and pembrolizumab administered every 3 weeks, on day 1 of each cycle. Absent relevant limiting toxicities, pembrolizumab may be administered even if cetuximab is to be held on day 1 for cetuximab related AEs. Likewise, in the instance of pembrolizumab related AEs which require dose holding or discontinuation, cetuximab administration should continue as appropriate. Cetuximab will be administered prior to pembrolizumab on day 1, due to concern for infusion reactions. Pembrolizumab may be administered on Day 2 of any cycle in the event of a Cetuximab related infusion reaction; or any other adverse event at the discretion of the PI.

If cetuximab is held for greater than 2 weeks for reasons other than cetuximab related adverse events, the 400 mg/m² loading dose may be readministered upon resumption, at the discretion of the investigator.

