6.1.1 Pembrolizumab

Dose Selection

Pembrolizumab 200 mg will be administered as a 30 minute IV infusion every 3 weeks. Sites should make every effort to target infusion timing to be as close to 30 minutes as possible. However, given the variability of infusion pumps from site to site, a window of 5 minutes and +10 minutes is permitted (i.e., infusion time is 30 minutes: -5 min/+10 min).

The package insert contains specific instructions for the preparation of the pembrolizumab infusion fluid and administration of infusion solution.

Timing of Dose Administration

Trial treatment will be administered on Day 1 of each cycle after all procedures/assessments have been completed (as detailed in **Table 4** Schedule of Procedures and Observations). Of note, the results of laboratory tests which are send-out tests (including TFTs) are not necessary prior to treatment. Pembrolizumab is to be administered after cetuximab infusion is complete. Trial treatment may be administered up to 3 days before or after the scheduled Day 1 of each cycle due to administrative reasons.

All trial treatments will be administered on an outpatient basis.

Pembrolizumab Dose Modification and Treatment Delay Guidelines

Adverse events (both non-serious and serious) associated with pembrolizumab exposure may represent an immunologic etiology. These adverse events may occur shortly after the first dose or several months after the last dose of treatment. Pembrolizumab must be withheld for drug-related toxicities and severe or life-threatening AEs as per **Table 1**. See **Section 6.3** and Events of Clinical Interest Guidance Document for supportive care guidelines, including use of corticosteroids

The following dose modification rules will be used with respect to potential toxicity. Toxicity will be assessed according to the NCI Common Terminology Criteria for Adverse Events Version 4.0 (CTCAE v4.0).

Table 1 Dose Modification Guidelines for Drug-Related Adverse Events: Pembrolizumab

Toxicity	Hold Treatment For Grade	Timing for Restarting Treatment	Discontinue Subject
Diarrhea/Colitis	2 ¹	Toxicity resolves to Grade \leq 1 ¹	Resume once improved to Grade \leq 1
	3	Toxicity resolves to Grade \leq 1	Toxicity does not resolve within 12 weeks of last dose or inability to reduce corticosteroid to 10 mg or less of prednisone or equivalent per day within 12 weeks
	4	Permanently discontinue	Permanently discontinue

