
Note: Permanently discontinue for any severe³ or Grade 3 drug-related AE that recurs or any life-threatening event.
 
¹ For grade 2 diarrhea which is attributed to cetuximab and sub-optimally managed with anti-diarrheal agents, Pembrolizumab may be continued. Patients should be seen in clinical follow-up within 1 week with additional phone follow-up within 72 hours. If optimally managed with anti-diarrheal agents and it is not felt that the toxicity is clearly cetuximab related, Pembrolizumab should be held until toxicity resolves to Grade \leq 1.
 
² For patients with liver metastasis who begin treatment with Grade 2 AST or ALT, if AST or ALT increases by greater than or equal to 50% relative to baseline and lasts for at least 1 week then patients should be discontinued.
 
³ Patients with intolerable or persistent Grade 2 drug-related AE may hold study medication at physician discretion. Permanently discontinue study drug for persistent Grade 2 adverse reactions for which treatment with study drug has been held, that do not recover to Grade 0-1 within 12 weeks of the last dose.
 
⁴ For these purposes, a severe toxicity is a toxicity which does not otherwise meet the criteria for grade 3 or 4, but which the investigator deems as being substantial enough to merit the holding of therapy.
 
⁵ For an acneiform or maculopapular rash which is deemed to be clearly related to cetuximab, at the investigator's discretion, pembrolizumab may be administered even for grade 3 rash, as long as the rash is showing signs of improvement and cetuximab is held as per protocol.
			

Dosing interruptions are permitted in the case of medical / surgical events or logistical reasons not related to study therapy (e.g., elective surgery, unrelated medical events, patient vacation, and/or holidays). Participants should be placed back on study therapy within 3 weeks of the scheduled interruption, unless otherwise discussed with the Sponsor. The reason for interruption should be documented in the patient's study record.

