6.3.13 Infusion Reactions

Signs and symptoms usually develop during or shortly after drug infusion and generally resolve completely within 24 hours of completion of infusion. **Table 3** shows treatment guidelines for participants who experience an infusion reaction associated with administration of pembrolizumab.

Table 3 Infusion Reaction Treatment Guidelines

NCI CTCAE Grade	Treatment	Premedication at subsequent dosing

Grade 1 Mild reaction; infusion interruption not indicated; intervention not indicated
	
Increase monitoring of vital signs as medically indicated until the subject is deemed medically stable in the opinion of the investigator.
	
None

Grade 2 Requires infusion interruption but responds promptly to symptomatic treatment (e.g., antihistamines, NSAIDS, narcotics, IV fluids); prophylactic medications indicated for <=24 hr.
	
Stop Infusion. Additional appropriate medical therapy may include but is not limited to:
 
 • IV fluids • Antihistamines • NSAIDS • Acetaminophen • Narcotics 
Increase monitoring of vital signs as medically indicated until the subject is deemed medically stable in the opinion of the investigator.
 
If symptoms resolve within one hour of stopping drug infusion, the infusion may be restarted at 50% of the original infusion rate (e.g., from 100 mL/hr to 50 mL/hr). Otherwise dosing will be held until symptoms resolve and the subject should be premedicated for the next scheduled dose.
 
Subjects who develop Grade 2 toxicity despite adequate premedication should be permanently discontinued from further trial treatment administration.
	
Subject may be premedicated 1.5 hr (\pm 30 minutes) prior to infusion of pembrolizumab (MK-3475) with:
 
 • Diphenhydramine 50 mg po (or equivalent dose of antihistamine). • Acetaminophen 500-1000 mg po (or equivalent dose of antipyretic).

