
Grades 3 or 4
 
Grade 3: Prolonged (i.e., not rapidly responsive to symptomatic medication and/or brief interruption of infusion); recurrence of symptoms following initial improvement; hospitalization indicated for other clinical sequelae (e.g., renal impairment, pulmonary infiltrates).
 
Grade 4: Life-threatening; pressor or ventilatory support indicated
	
Stop Infusion. Additional appropriate medical therapy may include but is not limited to:
 
 • IV fluids • Antihistamines • NSAIDS • Acetaminophen • Narcotics • Oxygen • Pressors • Corticosteroids • Epinephrine 
Increase monitoring of vital signs as medically indicated until the subject is deemed medically stable in the opinion of the investigator.
 
Hospitalization may be indicated.
 
Subject is permanently discontinued from further trial treatment administration
	
No subsequent dosing

Note: Appropriate resuscitation equipment should be available in the room and a physician readily available during the period of drug administration.

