12.3 Efficacy Analysis

Objective tumor response and six-month PFS will be tabulated and will be compared to the null values using exact tests. All treated patients with study therapy will be considered evaluable for response and 6-month PFS. Patients who receive at least one full dose of both drugs and come off study therapy prior to 6 months and receive off-protocol therapy will be considered treatment failures with regard to the 6-month PFS endpoint. Patients who have infusions reactions to cetuximab, such that continuation of treatment is not deemed feasible, will be replaced.

All patients treated with study therapy will be considered evaluable for response and 6-month PFS. Patients who come off study therapy prior to 6 months and receive off-protocol therapy will be considered treatment failures with regard to the 6-month PFS endpoint. Objective tumor response will not be considered after patient receives off-study therapy.

Objective tumor response using immune-related RECIST (irRECIST) will be tabulated.

Analysis of secondary endpoints will be hypothesis generating and descriptive in nature. Distributions of PFS and OS will be estimated using the Kaplan-Meier method.

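### After a pembrolizumab infusion reaction, Section 6.1 and Table 3 differ on whether cetuximab continues, and Section 12.3 can make the 6-month PFS score depend on which is followed

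*Combined protocol and SAP*

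**What the plan says.** Section 6.1 treats the two drugs separately: "in the instance of pembrolizumab related AEs which require dose holding or discontinuation, cetuximab administration should continue as appropriate".

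Table 3 (Section 6.3.13) is for "participants who experience an infusion reaction associated with administration of pembrolizumab". For Grade 3 or 4 it says: "Subject is permanently discontinued from further trial treatment administration". For Grade 2 it says: "Subjects who develop Grade 2 toxicity despite adequate premedication should be permanently discontinued from further trial treatment administration". Neither row makes an exception for cetuximab. Section 6.1.2, the cetuximab section, uses the term trial treatment for the infusions on Days 1, 8 and 15.

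Table 1 (Section 6.1.1, pembrolizumab) heads its last column "Discontinue Subject". Its footnote 2, on AST/ALT rises in patients with liver metastases, ends "lasts for at least 1 week then patients should be discontinued".

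Section 12.3 sets the endpoint rule: "Patients who come off study therapy prior to 6 months and receive off-protocol therapy will be considered treatment failures" for 6-month PFS. It also disregards response after off-study therapy. Section 6.6 ends disease follow-up when a non-study cancer treatment starts. None of these terms is defined for a patient who stops one drug and keeps the other. Section 7.4 says that cetuximab is commercially supplied, so the same drug can be given under the protocol or outside it.

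**The concern.** Take a patient whose pembrolizumab is stopped for an infusion reaction and who remains progression-free on cetuximab. A site following Section 6.1 continues cetuximab as protocol treatment, and the patient is scored on scans at month 6. A site following Table 3 as worded ends trial treatment. If cetuximab is then given commercially, it can be called off-protocol therapy, and Section 12.3 makes the patient a failure whatever the scans show. The same drug and the same disease course can give opposite scores.

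Six-month PFS is one of two primary efficacy endpoints, and activity on either is enough to recommend further study (Section 12.1). The ambiguity may also be beyond repair at analysis: if commercial cetuximab counts as a non-study cancer treatment under Section 6.6, disease follow-up stops and month-6 status may never be collected.

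**Working it through.** **1. The passages side by side, for one event: a pembrolizumab infusion reaction of Grade 3-4, or Grade 2 despite premedication**

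| Passage | Pembrolizumab | Cetuximab |
|---|---|---|
| Section 6.1 | stopped | continues, as appropriate |
| Table 3, with trial treatment as used in Section 6.1.2 | stopped | stopped |
| Section 12.3 | one-drug stop not classified | commercial cetuximab not classified |

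**2. Reproducing the design.** Inputs from Section 12.1: null rates 20% (response) and 30% (6-month PFS); alternatives 40% and 50%; 42 patients targeted, 38 required; type I error below 0.10; power at least 80%, 80% and 97%; endpoints independent. No cut-offs are stated, so I searched 10-15 responses and 14-20 PFS successes. With a and b the exact upper-tail binomial probabilities for the two endpoints, the chance of declaring activity is 1 - (1 - a)(1 - b).

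- n = 42, at least 14 responses or at least 18 progression-free. Null tails are 0.0298 and 0.0526, so type I error = 1 - 0.9702 × 0.9474 = 0.081. Power is 85.9% (response alone), 86.4% (PFS alone) and 97.9% (both).
- n = 38, at least 12 or at least 17. Null tails are 0.0623 and 0.0388, so type I error = 0.099. Power is 89.5%, 80.4% and 97.7%.

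At each of these two sample sizes this is the only pair in the search that meets every stated property. The plan's figures reproduce and are not in dispute.

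**3. Effect of miscoding.** Suppose k patients who are truly progression-free at 6 months are coded as failures. The PFS test then needs k more true successes. With PFS alone active (true rate 50%, response at 20%):

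| k | n = 42: PFS test | n = 42: either endpoint | n = 38: PFS test | n = 38: either endpoint |
|---|---|---|---|---|
| 0 | 86.0% | 86.4% | 79.1% | 80.4% |
| 1 | 78.0% | 78.6% | 68.6% | 70.6% |
| 2 | 67.8% | 68.8% | 56.4% | 59.1% |

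For example, at n = 42 and k = 1: 1 - 0.9702 × (1 - 0.7796) = 0.786. The null rejection rate of the PFS test at n = 42 falls from 0.053 to 0.026 (k = 1) and 0.012 (k = 2). This miscoding makes the test conservative; it does not create false positives.

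**4. How many patients.** The documents give no rate of pembrolizumab infusion reactions and no rate of stopping pembrolizumab before month 6. The infusion-reaction figure in Section 1.5 (up to 4.5%) is for cetuximab. So k is an assumption, shown as a range.

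**The case against.** **Table 3 can be read as drug-specific.** It sits under the supportive care guidelines for pembrolizumab, and Section 6.1.1 uses trial treatment for the Day 1 pembrolizumab schedule. The term may simply mean the drug under discussion. That reading is possible, but Section 6.1.2 uses the same term for cetuximab and Table 3 does not choose, so the wording still needs settling.

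**A reader might infer that Table 1 spreads the conflict to every pembrolizumab toxicity.** The documents do not support that. Table 1 is titled for pembrolizumab, its diabetes row speaks of holding and resuming pembrolizumab, footnotes 1 and 5 separate the two drugs, and cetuximab has its own Table 2. The column heading and footnote 2 are loose wording, not a clear contradiction.

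**A reader might put the affected number at 5-6 of 42**, from the 2 of 15 patients in Section 1.5 who stopped for adverse events (2/15 × 42 = 5.6). That cohort received gefitinib with an anti-PD-L1 antibody, and the count covers stops for any adverse event. It says nothing about pembrolizumab infusion reactions.

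**Stopping treatment is not itself a failure.** Section 12.3 also requires off-protocol therapy, and nothing in the documents says commercial cetuximab is the usual next step. The first paragraph of Section 12.3 further limits its failure rule to patients with at least one full dose of both drugs, which a first-infusion reaction may not meet; the second paragraph omits that limit. These points narrow the number affected but leave the ambiguity in place.

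**A reader might also infer that successes on cetuximab after pembrolizumab stops inflate the result.** The nulls are cetuximab-alone rates. A patient who behaves as if on cetuximab alone succeeds at the null rate, which dilutes an effect and does not manufacture one. Nor does such a patient become cetuximab-alone at once: the pembrolizumab half-life is 26 days (Section 1.4.1.2).

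**Conclusion.** The point holds, narrowly. For pembrolizumab infusion reactions of Grade 3-4, or Grade 2 despite premedication, Section 6.1 and Table 3 as worded give different instructions on cetuximab, and Section 12.3 can turn that difference into opposite 6-month PFS scores.

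The number of patients is probably small and cannot be estimated from the documents. The margin is also small: a single true success miscoded as a failure takes power with PFS alone active below the stated 80% at both 42 and 38 patients. This rests on the cut-offs inferred above, on independence of the endpoints, on commercial cetuximab being counted as off-protocol therapy, and on the patient actually receiving it. It deserves correction because the remedy is mainly wording. It is not evidence that the design or its sample size is wrong.

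**What to change.** 1. Reconcile Section 6.1 with Table 3 so that each states whether one drug or both stop, and tidy the Table 1 column heading and footnote 2 to match. The clinical choice is the sponsor's.

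2. In Section 12.3, state that the 6-month PFS failure rule is triggered by starting any anticancer therapy other than the two study drugs before month 6. Continuing cetuximab alone, protocol or commercial, does not trigger it and is scored on disease status. The rule should not require that both study drugs have stopped: a patient leaving on cetuximab plus chemotherapy would then escape it. Use the same definition where Section 12.3 disregards later responses.

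3. Apply that definition to non-study cancer treatment in Section 6.6, and keep the 9-weekly imaging until progression for these patients. Table 4 marks no imaging in its off-treatment or long-term follow-up columns, so the schedule needs a matching note.

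4. Report descriptively how many patients stopped pembrolizumab before month 6, and their outcomes. Do not recode them as failures against the unchanged cetuximab-alone null, which biases the result downward. As an illustration, 5 or 6 forced failures among 42 leave 37 or 36 patients to supply 18 successes; at a true 50%, power of the PFS test falls from 86% to 63% or 57%.

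The cost is a wording amendment, one descriptive table, and scans that continue for a few patients after trial treatment ends.

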6.1.1 Pembrolizumab

Dose Selection

Pembrolizumab 200 mg will be administered as a 30 minute IV infusion every 3 weeks. Sites should make every effort to target infusion timing to be as close to 30 minutes as possible. However, given the variability of infusion pumps from site to site, a window of 5 minutes and +10 minutes is permitted (i.e., infusion time is 30 minutes: -5 min/+10 min).

The package insert contains specific instructions for the preparation of the pembrolizumab infusion fluid and administration of infusion solution.

Timing of Dose Administration

Trial treatment will be administered on Day 1 of each cycle after all procedures/assessments have been completed (as detailed in **Table 4** Schedule of Procedures and Observations). Of note, the results of laboratory tests which are send-out tests (including TFTs) are not necessary prior to treatment. Pembrolizumab is to be administered after cetuximab infusion is complete. Trial treatment may be administered up to 3 days before or after the scheduled Day 1 of each cycle due to administrative reasons.

All trial treatments will be administered on an outpatient basis.

Pembrolizumab Dose Modification and Treatment Delay Guidelines

Adverse events (both non-serious and serious) associated with pembrolizumab exposure may represent an immunologic etiology. These adverse events may occur shortly after the first dose or several months after the last dose of treatment. Pembrolizumab must be withheld for drug-related toxicities and severe or life-threatening AEs as per **Table 1**. See **Section 6.3** and Events of Clinical Interest Guidance Document for supportive care guidelines, including use of corticosteroids

The following dose modification rules will be used with respect to potential toxicity. Toxicity will be assessed according to the NCI Common Terminology Criteria for Adverse Events Version 4.0 (CTCAE v4.0).

Table 1 Dose Modification Guidelines for Drug-Related Adverse Events: Pembrolizumab

Toxicity	Hold Treatment For Grade	Timing for Restarting Treatment	Discontinue Subject
Diarrhea/Colitis	2 ¹	Toxicity resolves to Grade \leq 1 ¹	Resume once improved to Grade \leq 1
	3	Toxicity resolves to Grade \leq 1	Toxicity does not resolve within 12 weeks of last dose or inability to reduce corticosteroid to 10 mg or less of prednisone or equivalent per day within 12 weeks
	4	Permanently discontinue	Permanently discontinue
AST, ALT, or Increased Bilirubin	2	Toxicity resolves to Grade \leq 1	Toxicity does not resolve within 12 weeks of last dose
	3-4	Permanently discontinue (see exception below) ²	Permanently discontinue
Type 1 diabetes mellitus (if new onset) or Hyperglycemia	T1DM or 3-4	Hold pembrolizumab for new onset Type 1 diabetes mellitus or Grade 3-4 hyperglycemia associated with evidence of beta cell failure	Resume pembrolizumab when patients are clinically and metabolically stable
Hypophysitis	2-3	Toxicity resolves to Grade \leq 1	Toxicity does not resolve within 12 weeks of last dose or inability to reduce corticosteroid to 10 mg or less of prednisone or equivalent per day within 12 weeks
	4	Permanently discontinue	Permanently discontinue
Hyperthyroidism	3	Toxicity resolves to Grade \leq 1	Toxicity does not resolve within 12 weeks of last dose or inability to reduce corticosteroid to 10 mg or less of prednisone or equivalent per day within 12 weeks.
	4	Permanently discontinue	Permanently discontinue
Infusion Reaction	3-4	Permanently discontinue	Permanently discontinue
Pneumonitis	2	Toxicity resolves to Grade \leq 1	Toxicity does not resolve within 12 weeks of last dose or inability to reduce

Toxicity	Hold Treatment For Grade	Timing for Restarting Treatment	Discontinue Subject
			corticosteroid to 10 mg or less of prednisone or equivalent per day within 12 weeks
	3-4	Permanently discontinue	Permanently discontinue
Renal Failure or Nephritis	2	Toxicity resolves to Grade \leq 1	Toxicity does not resolve within 12 weeks of last dose or inability to reduce corticosteroid to 10 mg or less of prednisone or equivalent per day within 12 weeks
	3-4	Permanently discontinue	
Rash³	3 or Severe ^{4,5}	Toxicity improves to Grade \leq 2	Toxicity does not improve within 12 weeks of last dose or inability to reduce corticosteroid to 10 mg or less of prednisone or equivalent within 12 weeks
All Other Drug-Related Toxicity,³	3 or Severe ⁴	Toxicity resolves to Grade \leq 1	Toxicity does not resolve within 12 weeks of last dose or inability to reduce corticosteroid to 10 mg or less of prednisone or equivalent per day within 12 weeks
	4	Permanently discontinue	Permanently discontinue

Note: Permanently discontinue for any severe³ or Grade 3 drug-related AE that recurs or any life-threatening event.
 
¹ For grade 2 diarrhea which is attributed to cetuximab and sub-optimally managed with anti-diarrheal agents, Pembrolizumab may be continued. Patients should be seen in clinical follow-up within 1 week with additional phone follow-up within 72 hours. If optimally managed with anti-diarrheal agents and it is not felt that the toxicity is clearly cetuximab related, Pembrolizumab should be held until toxicity resolves to Grade \leq 1.
 
² For patients with liver metastasis who begin treatment with Grade 2 AST or ALT, if AST or ALT increases by greater than or equal to 50% relative to baseline and lasts for at least 1 week then patients should be discontinued.
 
³ Patients with intolerable or persistent Grade 2 drug-related AE may hold study medication at physician discretion. Permanently discontinue study drug for persistent Grade 2 adverse reactions for which treatment with study drug has been held, that do not recover to Grade 0-1 within 12 weeks of the last dose.
 
⁴ For these purposes, a severe toxicity is a toxicity which does not otherwise meet the criteria for grade 3 or 4, but which the investigator deems as being substantial enough to merit the holding of therapy.
 
⁵ For an acneiform or maculopapular rash which is deemed to be clearly related to cetuximab, at the investigator's discretion, pembrolizumab may be administered even for grade 3 rash, as long as the rash is showing signs of improvement and cetuximab is held as per protocol.
			

Dosing interruptions are permitted in the case of medical / surgical events or logistical reasons not related to study therapy (e.g., elective surgery, unrelated medical events, patient vacation, and/or holidays). Participants should be placed back on study therapy within 3 weeks of the scheduled interruption, unless otherwise discussed with the Sponsor. The reason for interruption should be documented in the patient's study record.

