6.3.3 Type 1 Diabetes Mellitus or \geq Grade 3 Hyperglycemia

- Type 1 diabetes mellitus (T1DM), if new onset, including diabetic ketoacidosis (DKA)
- Grade 3 or higher hyperglycemia, if associated with ketosis (ketonuria) or metabolic acidosis (DKA)
- For **T1DM** or **Grade 3-4** Hyperglycemia
 - Insulin replacement therapy is recommended for Type I diabetes mellitus and for Grade 3-4 hyperglycemia associated with metabolic acidosis or ketonuria.
- Evaluate patients with serum glucose and a metabolic panel, urine ketones, glycosylated hemoglobin, and C-peptide.

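### After life-threatening hyperglycemia or ketoacidosis, the pembrolizumab dose-modification table gives opposite instructions: its row says to resume once stable, its note says to stop for good

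*Combined protocol and SAP*

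**What the plan says.** Section 6.1.1 makes its Table 1 the governing instruction: "Pembrolizumab must be withheld for drug-related toxicities and severe or life-threatening AEs as per" that table. (Section 6.1.2 also labels its dose-level table as Table 1; the pembrolizumab dose-modification table is the one meant here.)

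The row headed "Type 1 diabetes mellitus (if new onset) or Hyperglycemia" is triggered by new-onset type 1 diabetes or by Grade 3-4 hyperglycemia. The action is "Hold pembrolizumab for new onset Type 1 diabetes mellitus or Grade 3-4 hyperglycemia associated with evidence of beta cell failure". The cell in the column for discontinuing the subject reads "Resume pembrolizumab when patients are clinically and metabolically stable". There is no separate Grade 4 line.

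The note below the table orders permanent discontinuation for any severe "or Grade 3 drug-related AE that recurs or any life-threatening event". None of the table's five footnotes exempts the diabetes and hyperglycemia row.

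Section 6.3.3 covers the same events and expressly includes ketoacidosis, but gives only insulin and work-up guidance. It has no rule on restarting or stopping pembrolizumab. Section 6.3 sends the reader back to Section 6.1.1 for dose modification.

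**The concern.** The row and the note belong to the same table, and for one type of patient they cannot both be followed. If the hyperglycemia or ketoacidosis was life-threatening, the row has the site restart pembrolizumab once the patient is stable, and the note forbids any restart. No order of precedence is stated.

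The stake is patient safety: sites could make opposite re-exposure decisions after the same serious, possibly immune-related event, each with protocol text in support. Section 4.2 plans three sites. The adverse event profile is also a primary objective (Section 3.1), which is a further reason for handling such events in one way.

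**Working it through.** No arithmetic applies, so the check is a comparison of texts.

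**Step 1: how the other rows treat Grade 4.** Apart from the diabetes and hyperglycemia row, Table 1 has nine rows. Eight list Grade 4, alone or as Grade 3-4: diarrhea/colitis, liver tests, hypophysitis, hyperthyroidism, infusion reaction, pneumonitis, renal, and all other drug-related toxicity. All eight say to discontinue permanently; the liver row does so with a footnoted exception. The ninth, rash, has no Grade 4 entry. The diabetes and hyperglycemia row is thus the only one that lists Grade 4 and allows a restart without a marked exception.

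**Step 2: how the table marks exceptions.** The liver row points to a footnote. Diarrhea and rash have footnotes for events attributed to cetuximab. The diabetes and hyperglycemia row carries no footnote.

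**Step 3: what counts as life-threatening.** Section 10.2.1 defines the term for serious adverse events by immediate risk of death, not by grade. Table 3 in Section 6.3.13 has "Grade 4: Life-threatening; pressor or ventilatory support indicated", but for infusion reactions only. No grade definition for hyperglycemia is printed.

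**Step 4: row against note, case by case.** For hyperglycemia, the cases assume evidence of beta cell failure, as the row requires.

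| Event | Row | Note | Result |
|---|---|---|---|
| First Grade 3 hyperglycemia, not life-threatening | Hold, resume once stable | Not triggered | No conflict |
| New type 1 diabetes, not life-threatening, not recurrent | Hold, resume once stable | Not triggered | No conflict |
| New type 1 diabetes with life-threatening ketoacidosis | Hold, resume once stable | Stop permanently | Opposite |
| Grade 4 hyperglycemia, life-threatening | Hold, resume once stable | Stop permanently | Opposite |
| Grade 4 hyperglycemia, no immediate risk of death | Hold, resume once stable | Depends on whether Grade 4 alone counts as life-threatening | Unclear |
| Drug-related Grade 3 hyperglycemia that recurs | Silent on recurrence | Stop permanently | Note adds a limit; no contradiction |

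Two cases give opposite instructions and one cannot be settled from the text.

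**The case against.** The strongest defense is that row and note can be read together: hold and resume by default, but stop if the event was in fact life-threatening. The note's word for its scope, any, supports that, and Section 10.2.1 separates life-threatening from grade. A site could equally argue the reverse, that a specific row overrides a general note. Both readings are reasonable, they lead to opposite actions, and the text selects neither. The defense does succeed on one matter: Grade 4 hyperglycemia cannot simply be equated with a life-threatening event, because the documents print that equation only for infusion reactions.

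Three stronger readings are tempting, and the documents do not support them.

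- *A second Grade 3 event is also a contradiction.* The Grade 3 entries for diarrhea/colitis, hypophysitis, hyperthyroidism, rash and other toxicity also allow a restart and say nothing about recurrence. The note adds a recurrence limit to all of them. By the same logic every one of those rows would contradict it.
- *Any new type 1 diabetes is in conflict.* The note is reached only if the event is life-threatening, or is a severe or Grade 3 drug-related event that recurs. Resumption under the row is also conditional on stability.
- *The ambiguity could tip the 6-month PFS result.* Section 6.1 has cetuximab continue as appropriate when pembrolizumab is held or discontinued for its own toxicity. Under Section 12.3 a patient counts as a failure by this route only after both coming off study therapy before 6 months and receiving off-protocol therapy. Stopping pembrolizumab alone meets neither condition.

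Section 6.3 also refers to a separate guidance document on events of clinical interest, which was not available for this check. Even if it addresses the matter, Table 1 is the instruction that Section 6.1.1 names.

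**Conclusion.** The inconsistency is real but narrow. For life-threatening Grade 4 hyperglycemia or ketoacidosis, Table 1's row and its note give opposite instructions, with no stated precedence. For Grade 4 hyperglycemia without immediate risk of death, the instruction is unclear because the protocol does not say whether grade alone triggers the note.

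The event is expected to be rare; the documents give no rate, so none is estimated. For the patient affected the difference is complete: re-exposure or none. A reader might infer a consequence for response, 6-month PFS, power or type I error, but none is shown, because the link through Section 12.3 does not hold. The conclusion rests on the printed text of Table 1, its note and footnotes, and on Section 6.3.3 having no discontinuation rule. It takes no position on which instruction is clinically right.

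**What to change.** Reconcile the row and the note. Table 1 should state which of them governs Grade 4 hyperglycemia and life-threatening hyperglycemia or ketoacidosis, and whether Grade 4 alone counts as life-threatening for this row. For clarity, the same entry should say whether the note's recurrence rule applies to the row. The clinical choice belongs to the sponsor. Section 6.3.3 needs no matching change, since it has no discontinuation rule.

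The cost is one clarifying entry or footnote, made in an amendment with the ethics approval that Section 16.1 requires. Sample size, endpoints and analyses stay as they are.
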